7. STUDY DESIGN

Prospective cohort study to evaluate the diagnostic accuracy of SPCr and SACr in comparison with 24 hour proteinuria in hypertensive pregnant women with suspected proteinuria. We will also undertake decision analytic modeling and cost effectiveness analysis.

7.1 Primary outcome

The primary outcome is severe PE as defined by NICE [5]; women with severe hypertension (systolic BP ≥ 160 mmHg or diastolic BP ≥ 110 mmHg) and proteinuria or women with mild or moderate hypertension (systolic BP ≥ 140 mmHg and/or diastolic BP ≥ 90 mmHg) and proteinuria (≥ 300 mg/24-hour), with one or more of the following: severe headache, visual disturbances, problems with vision, severe pain just below the ribs or vomiting, papilloedema, signs of clonus (≥ 3 beats), liver tenderness, HELLP syndrome, platelet levels below $100 \times 10^9/L$, abnormal liver enzymes (ALT or AST >70 U/l).

We have chosen the primary outcome of severe PE because this is well accepted by clinicians and triggers clinical responses aimed at the safe delivery of the fetus whilst minimising maternal morbidity. All participating units in the study (and in the UK) have a clinical guideline for severe PE that is a core compliance standard for CNST (Clinical Negligence Scheme for Trusts) clinical risk assessment.

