5.3 Summary of current evidence

Current recommendations for assessment of proteinuria vary. Recently published NICE guidelines in the UK suggest the use of automated reagent-strip reading device to detect proteinuria. In women with a result of 1+ or more, the use of spot SPCr or 24 hour urine collection is recommended to quantify proteinuria. Significant proteinuria is defined as SPCr greater than 30 mg/mmol or a validated 24-hour urine collection greater than 300 mg/24 hour. Where 24-hour urine collection is used to quantify proteinuria, a recognized method of evaluating completeness of the sample is recommended [5]. The Society of Obstetricians and Gynaecologists of Canada suggests using urinary dipstick testing to screen for proteinuria, with the definition of significant proteinuria similar to NICE guidelines [11]. The American College of Obstetricians and Gynaecologists consider 24 hour urine protein estimation of more than 300 mg as significant proteinuria for a diagnosis of PE [12].

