6. AIMS OF THE STUDY

Our proposed study evaluates the measurement of proteinuria in women with suspected preeclampsia (PE). This includes women with gestational hypertension $\geq 140/90$ mmHg and \geq Trace proteinuria on automated dipstick analysis.

Primary Objectives:

1. To evaluate the diagnostic accuracy of quantitative assessments of SPCr and SACr (index tests) at different thresholds in predicting severe PE compared to 24 hour urine protein measurement

Secondary Objectives:

2. To assess the accuracy of point of care assessments of SPCr and SACr at different thresholds in diagnosing PE compared to 24 hour urine protein measurement
3. To identify the laboratory assay method of 24 hour proteinuria that is most accurate in the assessment of PE
4. To estimate the accuracy of both quantitative and point of care assessments of SPCr and SACr at different thresholds in predicting adverse fetal outcomes
5. To estimate the diagnostic utility of SPCr or SACr as a potential replacement for 24 hour protein estimation by developing a decision analytic model
6. To assess the cost effectiveness using cost per correct diagnosis and cost per adverse outcome predicted as key measures

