7.2 Secondary clinical outcomes

Maternal: Diagnosis of PE using a 24 hour proteinuria threshold of 300 mg/24 h

Fetal: Composite adverse perinatal outcome identified by Delphi survey of clinicians. This includes one or more of the following: perinatal or infant mortality, bronchopulmonary dysplasia, necrotising enterocolitis, grade III/IV intraventricular haemorrhage, cystic periventricular leukomalacia, or stage 3-5 retinopathy of prematurity and hypoxic ischaemic encephalopathy.

Costs: Health service data on bed use, surveillance visits as an inpatient, outpatient and peripartum health service resource use related to delivery, postnatal care and follow-up tests will be collected by the research midwife following delivery. These will include resource use for neonatal care. (see section 7: Economic evaluation).

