12.2 Analysis

We aim to show that a quantitative assessment of SPCr or SACr can safely rule out the possibility of adverse outcomes. Diagnostic accuracy of laboratory and POC care measurements of SPCr and SACr at given cut-offs will be summarised using sensitivity, specificity, and positive and negative likelihood ratios, estimated using standard methods for proportions. Sensitivity and specificity at different cut-offs will be used to plot non-parametric receiver operating characteristic (ROC) curves for the different assays. Laboratory quantitative assessments of SPCr and SACr, POC are assays, and laboratory measures of 24-hour urine protein will be compared by looking at the difference between the areas under the respective ROC curves. Caution should be exercised if an ROC curve is used to select an “optimal” cut-off for a continuous test measure without validation in a separate sample. We will use our sample to validate cut-offs identified in previous research [7]. By restricting analyses to those women with 1+ or higher on the automated dipstick test, we will evaluate test performance in the population of women who would currently be referred for further testing. Because we may wish to consider making testing more inclusive, we will also analyse our entire sample to evaluate test performance in women with trace or higher on the automated dipstick test.

In addition we will use linear regression to explore the relationship between each SPCr/SACr measurement and the local measurement of 24-hour proteinuria (“linear” regression in the sense of a Normal model with linear link function; we will have a large enough sample to investigate non-linear associations between SPCr/SACr and 24-hour proteinuria). In particular, we will investigate whether the relationship is different at sites using different 24-hour assays, and whether these differences might be explained by measured patient characteristics. If there are differences between sites, our primary analysis of diagnostic accuracy will be stratified by the type of 24-hour assay used. To make use of the full sample, and to try and obtain more generalizable results, we will also fit multivariable logistic regression models for predicting outcomes using SPCr/SACr, site, and patient characteristics.

All analyses will be carried out using Stata v11 (Stata Corporation, College Station, Texas USA).

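### 24-hour protein is both the comparator and part of the outcome, so the ROC comparison favours it over SPCr/SACr, and objective 3 is circular as written

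*Protocol*

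**What the plan says.** The primary objective (Section 6) is the accuracy of quantitative SPCr and SACr "at different thresholds in predicting severe PE compared to 24 hour urine protein measurement". Section 12.2 carries this out by ROC curves: the laboratory and point-of-care assays "and laboratory measures of 24-hour urine protein will be compared by looking at the difference between the areas under the respective ROC curves".

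Severe PE (Section 7.1) has two limbs. The first is "women with severe hypertension (systolic BP ≥ 160 mmHg or diastolic BP ≥ 110 mmHg) and proteinuria", with no test or threshold named. The second is mild or moderate hypertension "and proteinuria (≥ 300 mg/24-hour), with one or more of the following: severe headache", followed by the other listed symptoms, signs and blood results.

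The secondary maternal outcome (Section 7.2) is "Diagnosis of PE using a 24 hour proteinuria threshold of 300 mg/24 h", with no assay named. Objective 3 (Section 6) is "To identify the laboratory assay method of 24 hour proteinuria that is most accurate in the assessment of PE".

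Section 5.3 reports the guideline on which the primary outcome rests: "Significant proteinuria is defined as SPCr greater than 30 mg/mmol or a validated 24-hour urine collection greater than 300 mg/24 hour". Section 9 describes SPCr above 30 mg/mmol as a clinical diagnosis of PE.

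**The concern.** A test cannot be compared fairly with another when one of them helps to decide who is a case (incorporation bias). In the mild/moderate limb no woman can be a case unless her 24-hour protein reaches 300 mg. The 24-hour measurement that sets case status therefore has 100% sensitivity at that cut, and no spot test can do better.

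Three things are at stake. A spot test that is as good as 24-hour protein, or better, may look worse, although Section 5.2 seeks a replacement that is at least equivalent. Objective 3 would return whichever assay was used to define PE. And high index-test sensitivity for severe PE could be taken to show prediction of the severe clinical features when part of it is detection of proteinuria.

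**Working it through.** **1. The plan's own figure.** Section 12.1 asks for 240 women with severe PE (null sensitivity 90%, true sensitivity 95%, 80% power, 95% confidence limits):

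n = [(1.960 × √(0.90 × 0.10) + 0.842 × √(0.95 × 0.05)) / 0.05]² ≈ 238.0, rounded up to 239.

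The figure reproduces to within one woman. It contains no term for 24-hour protein, so the sized claim concerns index-test sensitivity alone and not the contrast with the comparator.

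**2. Where the overlap lies.**

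| Outcome | Role of 24-hour protein in the definition | Overlap with the comparator |
|---|---|---|
| PE (7.2) | The stated laboratory criterion | Full |
| Severe PE, mild/moderate limb (7.1) | Required, with a clinical feature | Partial |
| Severe PE, severe-hypertension limb (7.1) | Proteinuria, test not named | Open |
| Perinatal composite (7.2) | None | None |

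**3. PE.** A case is a woman with 24-hour protein of at least 300 mg. For the assay that sets this cut, sensitivity = specificity = AUC = 1, with no assumption needed. In an illustrative simulation (400,000 women per scenario, normal latent scale), a second assay correlating 0.95 with the defining one reached an AUC of only 0.969 to 0.973. Objective 3 would therefore rank it second for that reason alone. No section says which assay defines PE, although Section 5.4 reports prevalence above 300 mg of 24.9% with one assay and 70.1% with another.

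**4. Severe PE, 24-hour protein.** Assumptions: the 300 mg threshold applies to both limbs; severe PE is 15.6% (the proxy figure in Section 12.1); PE prevalence is 24.9% or 70.1% (Section 5.4), with 45% as an assumed middle value; and the severe features are unrelated to protein. On the features alone every test then has an AUC of 0.50. On severe PE as defined:

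- specificity at 300 mg = (1 − PE prevalence) / (1 − 0.156)
- AUC = specificity + (1 − specificity)/2 = (1 + specificity)/2, because non-cases below 300 mg always rank below cases and the remaining non-cases rank at random against them.

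| PE prevalence | Specificity | AUC |
|---|---|---|
| 24.9% | 0.751/0.844 = 0.890 | 0.945 |
| 45% | 0.550/0.844 = 0.652 | 0.826 |
| 70.1% | 0.299/0.844 = 0.354 | 0.677 |

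The simulation gives 0.945–0.946, 0.825–0.826 and 0.675–0.678. A marker with no relation to the severe features thus gains an AUC of 0.68 to 0.95 from the definition.

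**5. Severe PE, the gap to the index test** (same simulation, index test correlating 0.7 or 0.9 with 24-hour protein, an assumption):

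| PE prevalence | Gap, correlation 0.7 | Gap, correlation 0.9 |
|---|---|---|
| 24.9% | 0.946 − 0.804 = 0.142 | 0.945 − 0.898 = 0.047 |
| 45% | 0.826 − 0.715 = 0.111 | 0.825 − 0.786 = 0.039 |
| 70.1% | 0.678 − 0.621 = 0.057 | 0.675 − 0.655 = 0.020 |

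On the features alone the true gap is 0. If the features correlate 0.3 with 24-hour protein, the gap for severe PE is 0.027 to 0.138, against 0.014 to 0.045 on the features alone.

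**6. Two equally accurate tests.** A second simulation took log-normal protein with median 300–450 mg and log-SD 0.9–1.2, equal test error SD of 0.25–0.4, features modestly related to protein, and the 300 mg rule applied to every case. 24-hour protein gained 0.008 to 0.051 in AUC, and its sensitivity was 100% against 84–96% for the spot test. With protein removed from the outcome the AUC gap was 0.000.

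**7. What is not affected.** Objective 2 uses 24-hour protein as the reference standard for point-of-care tests, which is ordinary diagnostic accuracy. Objective 4 uses a composite without proteinuria.

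**The case against.** Several counter-arguments have force.

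- Only one limb of severe PE carries the 300 mg threshold. This stands: the overlap is partial, and both simulations, which apply the threshold to every case, model a stricter outcome than the protocol states. If SPCr above 30 mg/mmol were accepted as proteinuria in the other limb, as Section 5.3 would allow, SPCr itself would gain there.
- A reader might infer that index-test accuracy is inflated. The documents do not support this as a statement about severe PE. In the mild/moderate limb the incorporated measurement is the comparator, so the head-to-head is conservative for the spot tests. In the second simulation spot-test sensitivity falls from 84–96% to 57–81% on the features alone, but that reflects a change of target condition.
- A reader might also infer that the economic model receives a near-perfect 24-hour arm. For severe PE this does not follow: step 4 gives specificity of 0.35 to 0.89.
- Section 9 says that blood pressure and proteinuria results up to 6 weeks postnatal confirm the diagnosis, so the recruitment collection need not be the one that decides. This stands as a caveat: the 100% sensitivity belongs to whichever measurement sets case status. The protocol does, however, schedule only one 24-hour collection.
- Supplementary analyses may be in an analysis plan that is not shown. That is possible, but the outcome definitions and the wording of objective 3 are fixed in this protocol.

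Concealing results from clinicians (Section 7.3.3) and stratifying by assay (Section 12.2) do not remove a shared outcome component.

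**Conclusion.** The point holds in a limited form and should be fixed. The comparison of SPCr/SACr with 24-hour protein has full incorporation for PE and partial incorporation for severe PE. Wherever the 24-hour threshold sets case status, the direction is certain: it favours 24-hour protein. In the severe-hypertension limb it stays open until the measurement is named. Objective 3 cannot be answered against PE as defined in Section 7.2.

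The size for severe PE is not known. The range of about 0.01 to 0.14 in AUC rests on assumed distributions, correlations and error, and on applying 300 mg to both limbs.

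It would go too far to say that the primary claim fails. Index-test sensitivity for severe PE is a valid estimate for that outcome, and the 240 cases are sized for it. It should not be read as accuracy for severe hypertension, symptoms, HELLP, platelets or liver enzymes on their own.

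**What to change.** 1. Keep severe PE as defined by NICE as the primary outcome.
2. In Sections 7.1 and 7.2, state which measurement, which collection and which assay establishes proteinuria in each limb of severe PE and in PE.
3. In Section 12.2, name the outcome for each ROC comparison. Report the head-to-head comparisons with 24-hour protein also on a protein-free version (severe hypertension or at least one listed feature, whatever the 24-hour result) and on the perinatal composite. Do not present 24-hour protein as a competing test for PE.
4. Restate objective 3 so that the benzethonium chloride and pyrogallol red assays are compared on those protein-free outcomes. Section 5.4 shows the applicants have already judged assays this way, on severe hypertension, birthweight and biochemical disease.

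The cost is rewording and extra analysis, with no more participants, provided that blood pressure and the listed features are recorded for every woman whatever her proteinuria. The drawback is that the protein-free outcome also counts severe gestational hypertension without PE, so it supplements the primary outcome and does not replace it.

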7.2 Secondary clinical outcomes

Maternal: Diagnosis of PE using a 24 hour proteinuria threshold of 300 mg/24 h

Fetal: Composite adverse perinatal outcome identified by Delphi survey of clinicians. This includes one or more of the following: perinatal or infant mortality, bronchopulmonary dysplasia, necrotising enterocolitis, grade III/IV intraventricular haemorrhage, cystic periventricular leukomalacia, or stage 3-5 retinopathy of prematurity and hypoxic ischaemic encephalopathy.

Costs: Health service data on bed use, surveillance visits as an inpatient, outpatient and peripartum health service resource use related to delivery, postnatal care and follow-up tests will be collected by the research midwife following delivery. These will include resource use for neonatal care. (see section 7: Economic evaluation).

7.3 Baseline assessments

For eligible women clinical details will be collected to confirm eligibility and that written consent has been obtained.

7.3.1 Collection of outcome data

Clinical data, on both mother and baby, will be collected at birth and discharge from hospital from the hospital case notes on to a DAPPA Data Collection Form (DCF). This will include those babies who are admitted to the NICU.

7.3.2 Women or Babies that are transferred

If a study woman or baby is transferred to another hospital the Study Office will be informed so that all women and babies can be followed up until discharge or death. Each transfer hospital will be asked to provide information relating to any of the Study outcomes that may have occurred during the women or babies stay in that hospital.

7.3.3 Minimisation of bias

The Study is prospective and observational and only those urinalysis results currently in clinical use will be revealed to clinicians. Other tests of proteinuria will be either blinded to clinicians or performed in batches after clinical management decisions have been made on stored samples.

Loss to follow-up for the clinical data will be negligible as this information will be collected before the woman is discharged from hospital. Neonatal outcome data for the small number of babies admitted to the neonatal unit will be collected through the midwives employed in each unit. Should either the woman or babies be transferred to another neonatal unit, data will be collected from all the hospitals that provide their care.

Loss of data regarding the health economic data collected at a week and 6 weeks from the woman will be minimised by the development of robust systems to maximise response rates.

7.4 Duration of study

This study will start in September 2012 and be completed at the end of April 2016. This includes a 6 month start-up phase to obtain permissions from MHRA, Multicentre Research Ethics Committee and local Research and Development Offices, together

with the development of data collection tools and questionnaires. Computer systems will be developed towards the end of this to support the collection of data outcomes.

We will have up to a total of 36 recruiting Maternity Units by December 2014. Accurate assessment of the numbers of women eligible, approached and recruited will be made and we anticipate that up to 70 women will be recruited per month.

Recruitment will finish in the Maternity Units at the end of November 2015. A further 6 months has been allowed for the analysis of the data obtained, with a 3 month extension for the submission date of the final report to the funder. The new funding contract end date will be 31 July 2016, with the final report to funder due in August 2016

7.5 Details of study design and procedures

This is a prospective cohort study to evaluate the diagnostic accuracy of SPCr and SACr in comparison with 24 hour proteinuria in hypertensive pregnant women with suspected proteinuria. We will also undertake decision analytic modeling and cost effectiveness analysis.

[figure not shown]

Figure 1: Flow chart for study design

8. HEALTH TECHNOLOGIES BEING ASSESSED

8.1 Index tests

Laboratory quantitative tests (Laboratory SPCr and SACr)

Urinary protein will be measured using a benzethonium chloride turbidimetric method in all recruiting hospitals. The reagent acts as a denaturing agent causing the formation of a fine suspension in the reaction mixture. The analytical range for the Benzethonium chloride assay is 68 to 2000 mg/L and the day-to-day precision is 1.4 – 3.0%.

The SACr will be measured using an automated chemistry analyzer. Albumin is measured using an immunoturbidimetric immunoassay. The analytical range of the assay is 5 to 500 mg/L, and the day-to-day precision is within the range 2.5 – 5.0%. The analytical range of the assay is 0.3 to 44.2 mmol/L and the day-to-day precision is between 1.5 – 3.0%.

The urine creatinine will be measured using an enzymatic reaction, in which creatininase hydrolyses creatinine to creatine, which is itself hydrolysed by creatinase to sarcosine and urea. The analytical range of the assay for SPCr is 0.3 to 44.2 mmol/L and the day-to-day precision is between 1.5 – 3.0%.

Point of Care tests (Semi quantitative reagent strip SACr).

The dipstick test for ACR comprises two test pads, the colours formed in the presence of albumin and creatinine being read using a reflectance meter; the system provides a semi-quantitative result. The detection of albumin is based on binding of Bis (3',3''-diiodo-4',4''-hydroxy-5',5''-dinitrophenyl)-3,4,5,6-tetrabromosulfonephthalein (DIDNTB) at pH 1.5. It has been shown to be specific for the detection of albumin. The detection limit of the method is 0.9 mmol/L (10 mg/dl). The ACR is reported as one of the following ranges in conventional units (mg/g): <30, 30-300; or >300; or one of the following ranges in SI units (mg/mmol): <3.4, 3.4-33.9, or >33.9.

8.2 Comparative tests (24 hour proteinuria and 24 hour albuminuria)

The measurement of the total protein concentration in urine is difficult for several reasons. The quantity of total protein is much lower in urine than in serum and there is large sample-sample variation, as well as interference from non-protein substances [18]. There are a number of different assays for measuring urinary total protein. Most laboratories in the UK currently use turbidimetric or colorimetric assays. The two most common methods employed are the benzethonium chloride and pyrogallol methods; for this reason we plan to study the variation of performance of these two methods to give an overview of the variation found between laboratories. Either a protein or albumin concentration or a fully quantitative SPCr or SACr can be reported.

Total Protein will be measured using a benzethonium chloride turbidimetric method in our secondary reference lab to explore inter-laboratory variation from the recruiting centres. Additionally, total protein will be measured using the Pyrogallol Red method (Sigma, Saint Louis, Missouri, USA) on a Cobas Mira Plus (Roche Diagnostics, Basel, Switzerland). In the assay, a pyrogallol red-molybdate complex binds to basic amino acid groups of protein molecules causing an increase in absorbance measured at 600 nm. The analytical range of the assay is stated by the manufacturer to be 10 to 2000 mg/L urinary total protein.

9. STUDY CONDUCT

All eligible women will be invited to participate at each site. Women will be given trial information by the research midwife and a Participant Information Sheet (PIS) to keep, and then subsequently recruited following obtaining written consent.

As part of routine clinical care women are asked to provide a urine sample for protein analysis. In those women who consent to taking part in this study, an aliquot of the spot urine sample will be collected and stored at -80°C. This spot urine will then be sent for a laboratory SPCr. Clinical management will be determined at this point based on the automated urine dipstick result and SPCr (as per routine practice). Women will then be asked to collect a 24 hour urine sample as either an in-patient or outpatient, dependent on the clinical care plan (as per NICE CG107) [5]. Those women with trace proteinuria and a SPCr <30mg/mmol (i.e. without clinical PE) will collect as an outpatient and those with a SPCr of >30 mg/mmol (i.e. with a clinical diagnosis of PE) will collect as an in-patient. An aliquot of this 24-hour urine sample will be stored at -80°C for secondary analysis. Clinical management will be determined from the automated dipstick, the local laboratory SPCr and /or the local laboratory 24 hour urine collection performed locally.

Immediately prior to delivery, a further spot sample of urine will be taken and stored for later analysis. This will allow the maximum proteinuria level to be calculated as well as the increase in proteinuria from initial presentation.

Women will be followed up until 6 weeks postnatal when their blood pressure and proteinuria results (from either hospital / primary care clinics) will confirm their pregnancy diagnosis. At this point a detailed collection of outcome data will be performed by the research midwife. Data will be abstracted from the hospital records for the maternal and neonatal outcomes at birth and discharge home.

The aliquots of urine will be sent in batches for secondary analysis at East Kent Hospitals Trust of 24-hour total albumin excretion by 2 different assays. The spot urine sample will also be tested using point of care testing for SPCr (semi-quantitative dipstick); POC SACr (semi-quantitative dipstick); and POC SACr (fully quantitative test). All data will be entered into a clinical data management software package supplied by MedSciNet configured to allow web-based entry from each of the seven clinical sites as well as the secondary analysis laboratory.

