5.2 Description of Technology

Index tests: Proteinuria estimation by urinary SPCr or urinary SACr in women with suspected PE is available as either a laboratory or point of care (POC) test. The POC SPCr and SACr are measured by urine reagent strip analysis on a semi-quantitative automated reader. SACr can also be measured on a fully quantitative device configured in a plastic cassette, the reaction being monitored in a benchtop photometer. These technologies are already in clinical use for screening albuminuria (and microalbuminuria) and proteinuria in both chronic kidney disease and diabetes.

Comparative test: Measurement of 24-hour urine protein is currently the gold standard for the assessment of proteinuria in pregnancy. However this test is associated with

significant costs related to hospital admission, as often women are admitted as an inpatient for up to 48 hours until the results become available. Furthermore, the measurement is subject to errors (in as many as 20% of patients) as a result of incomplete collection. Diagnosis of proteinuria in HDP also varies with the type of laboratory assay used [4].

A reliable, accurate and cost effective SPCr or SACr ratio test (laboratory or POC), that is equivalent or better than 24 hour protein estimation at predicting adverse maternal and fetal outcomes, could be employed as the primary test in the assessment of women with suspected PE. Furthermore, given the rising costs of inpatient care, the use of SPCr or SACr has the potential to deliver significant cost improvements. A clearer understanding of the threshold of proteinuria (by any measurement) that predicts increased risks of adverse maternal and fetal outcomes will allow the concentration of scarce NHS resource onto the more intensive monitoring of fewer women.

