12. STATISTICS

12.1 The Revised Sample size Calculation

The sample size for the study was determined in order to show that a quantitative assessment of SPCr or SACr at a given cut-off can safely rule out the possibility of severe PE. In diagnostic testing terms, the test should have a LR- of 0.1 or smaller, and a sensitivity of at least 90% with high specificity. Previous studies suggest that SPCr or SACr (when fully quantitative), might achieve this.

To demonstrate with 80% power that sensitivity is at least 90% within 95% confidence limits, assuming that sensitivity is actually 95%, requires 240 women with severe PE.

In an interim analysis of the first 500 recruited women we found 78 who met a proxy definition of severe PE (primary outcome data not yet being available for most participants) – that is, a prevalence of 15.6%. This estimate is likely to be conservatively low, as 81 women (16.2%) out of the first 500 recruited women did not have enough data currently available to determine even the proxy outcome. Allowing for 14% of participants to have missing data on the primary outcome in the final analysis, we therefore need to recruit 1710 women with gestational hypertension and suspected PE to the study. We have based this 14% estimate on the preliminary analysis of the first recruited 1200 women.

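### The 24-hour collection, which the protocol says is often incomplete, has no planned study check of completeness, although the collection setting partly follows the SPCr result

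*Protocol*

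**What the plan says.** **Known weakness of the reference measurement.** Protocol section 5.2 says of 24-hour urine protein that "the measurement is subject to errors (in as many as 20% of patients) as a result of incomplete collection". Section 5.3, summarising the national guideline, reports that where a 24-hour collection is used "a recognized method of evaluating completeness of the sample is recommended".

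**Where the 24-hour result is used.**
- Section 7.1: proteinuria is part of the definition of severe PE. The mild or moderate hypertension route names the 300 mg/24-hour threshold; the severe hypertension route says only that proteinuria is present.
- Section 7.2: PE is diagnosed at 300 mg/24 h.
- Section 12.2: 24-hour protein is one of the tests whose ROC areas are compared, and the local 24-hour value is the variable to which SPCr and SACr are related by regression.

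**How it is collected.** Section 9: "Those women with trace proteinuria and a SPCr <30mg/mmol (i.e. without clinical PE) will collect as an outpatient". Women with SPCr above 30 mg/mmol collect as in-patients.

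**What is planned on the sample.** Sections 8.2 and 9 plan protein and albumin assays on the stored 24-hour aliquot. Section 8.2 adds that a protein or albumin ratio can be reported, which would need a creatinine value, but nothing links creatinine or urine volume to completeness. Section 12.2 contains no analysis that uses completeness.

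**Missing outcomes.** Section 7.3.3 says "Loss to follow-up for the clinical data will be negligible". Section 12.1 sizes the study "Allowing for 14% of participants to have missing data on the primary outcome in the final analysis".

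**The concern.** Sensitivity is the share of true severe-PE cases that the index test detects. An incomplete collection can read below 300 mg/24 h and so take a true case out of that denominator. If this happens at the same rate in index-positive and index-negative women, sensitivity does not move. If the rates differ, it does. Because section 9 lets SPCr help decide where the reference sample is collected, the protocol opens a route by which the rates could differ, and it plans no measurement that would show whether they did.

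The claim at stake is a rule-out claim. Section 12.1 requires that "the test should have a LR- of 0.1 or smaller, and a sensitivity of at least 90% with high specificity". An error that makes false negatives look like non-cases would favour the claim in the unsafe direction. Two other results are exposed whatever the direction: prevalence and accuracy for PE at 300 mg, and the ROC area of the 24-hour test. Under-collection adds noise to the 24-hour test, which by itself makes the spot tests look better beside it.

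**Working it through.** **1. The plan's own figure.** Section 12.1 aims "To demonstrate with 80% power that sensitivity is at least 90% within 95% confidence limits", and "assuming that sensitivity is actually 95%, requires 240 women with severe PE". With p0 = 0.90, p1 = 0.95, two-sided 5% and 80% power:

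n = [(1.960 × √(0.90 × 0.10) + 0.8416 × √(0.95 × 0.05)) / 0.05]² = 238.03, so 239.

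The stated 240 is reproduced. With 240 cases, at least 226 must be detected (226/240 = 0.942) for an exact lower 95% limit of 0.90 or more.

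**2. Effect of losing cases.** Let S be true sensitivity, and a and b the shares of true severe-PE cases lost from the case group among index-positive and index-negative women. Then

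apparent sensitivity = S(1 − a) / [S(1 − a) + (1 − S)(1 − b)].

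The protocol gives no loss rate by setting or by SPCr, so a and b are assumptions. With S = 0.90:

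| a (index-positive) | b (index-negative) | Apparent sensitivity | Chance of meeting the criterion with 240 analysed cases |
|---|---|---|---|
| 20% | 10% | 0.72/(0.72 + 0.09) = 0.889 | 0.4% |
| equal | equal | 0.900 | 1.5% |
| 10% | 20% | 0.81/(0.81 + 0.08) = 0.910 | 4.9% |
| 5% | 20% | 0.855/(0.855 + 0.08) = 0.914 | 7.6% |
| 0 | 20% | 0.90/(0.90 + 0.08) = 0.918 | 11.1% |
| 0 | 40% | 0.90/(0.90 + 0.06) = 0.938 | 46% |

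The last column is the binomial probability of 226 or more out of 240 at the apparent sensitivity. Read backwards, an apparent 0.90 with a = 0 and b = 20% corresponds to a true 0.878.

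**3. How far an incomplete sample moves a woman across 300 mg.** If a fraction r of the urine is recovered, the sample reads below 300 mg whenever true excretion is below 300/r: 333 mg at r = 0.9, 429 mg at r = 0.7 and 600 mg at r = 0.5. Only women between 300 mg and that value are reclassified. To give a scale, assume log-normal excretion with median 350 mg and log-SD 1; neither figure is in the protocol. Among women truly at or above 300 mg who have an incomplete sample, 7% (r = 0.9), 25% (r = 0.7) or 47% (r = 0.5) then read below 300 mg. With r spread evenly from 0.5 to 0.9 the figure is 26%. If 20% of collections are incomplete, that is 0.20 × 26% = 5.2% of all women truly at or above 300 mg, with a range of 1.5% to 9.5%. This concerns PE at 300 mg. It gives no split by SPCr result, so it implies no particular shift in sensitivity for severe PE.

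**4. Does the text supply a and b?** No. The 20% in section 5.2 is a background upper figure, not divided by setting, and nothing says which setting gives fuller collections.

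**The case against.** **Guideline care covers completeness.** Section 5.3 refers to a validated collection, section 9 ties collection to the guideline care plan, and section 15.1 asks sites to follow that guideline. This softens the point: some sites may well check. It does not give the study a recorded completeness variable, so the analysis cannot use one.

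**Nothing says that home collections are worse.** Correct. A reader might infer that outpatient samples are less complete and that rule-out sensitivity is therefore overstated. The documents do not support that. Section 5.2 gives its error figure just after describing in-patient admission, and section 5.1 says testing is mostly done on in-patients. The direction must be left open.

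**The affected group is limited.** The outpatient rule covers trace proteinuria with SPCr below 30 mg/mmol. The analysis in section 12.2 restricted to 1+ or more leaves those women out. SACr does not set the place of collection. The severe-hypertension route in section 7.1 names no 24-hour threshold, and the other route also needs clinical or laboratory features. All of this stands and narrows the effect on severe PE. The full-sample analysis, the PE outcome and the ROC comparison remain exposed.

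**The plan may discard the 14% with missing outcomes.** A reader might infer this and expect a verification bias from it. The protocol only enlarges the sample for missing outcomes; it does not say that these women are dropped, and how they are handled is a matter for the SAP, which is not shown. Nor are sections 7.3.3 and 12.1 in plain conflict: one concerns follow-up, the other the primary outcome, which can also be missing for want of a urine or blood result. That is a point of wording.

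**Conclusion.** The point holds as a gap in measurement, not as a demonstrated bias. The protocol names incomplete collection as a common fault of its comparator, reports the recommended safeguard, uses the 24-hour result in the primary outcome, the PE outcome and the ROC comparison, and plans neither a study measure of completeness nor an analysis that uses one. Because SPCr partly decides the setting, error that differs by index result is possible and would go unseen.

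Under the assumed loss rates, a true sensitivity of 0.90 reads between 0.889 and 0.938, and stays at 0.900 if losses are equal. Losing 20% of index-negative cases and no index-positive cases gives 0.918. The sign and size in this study cannot be known from the documents. Since only women within reach of 300 mg are reclassified, the share of cases lost will generally be smaller than the share of incomplete collections.

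This belongs in the protocol because the protocol decides what is assayed: an SAP cannot analyse a creatinine value that nobody measured.

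**What to change.** 1. Add creatinine to the assays on the stored 24-hour aliquot, using the enzymatic method already described in section 8.1, and record the collection volume, which is needed in any case to express protein per 24 hours.
2. Define in advance a rule on creatinine excretion and volume that flags a collection as incomplete.
3. Report the flag rate by collection setting and by SPCr result. This table shows which row of the calculation above is plausible.
4. Repeat the accuracy and ROC analyses without flagged collections, as a sensitivity analysis. Read it beside the table in item 3: if flag rates differ by SPCr result, exclusion itself shifts sensitivity by the same formula, with the flag rates among cases in place of a and b.
5. Reword section 7.3.3 so that it agrees with the 14% missing primary outcome allowed for in section 12.1.

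The cost is one inexpensive assay per stored sample, one more recorded field, and fewer women in the sensitivity analysis, hence wider intervals there. Patient care does not change.
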